8.3 Data Analysis Plans

A patient will be considered an evaluable study subject evaluable for data analysis per the following criteria, a written informed consent was obtained, he meets the inclusion and exclusion criteria, and received the PAE study procedure. All subjects with 12-month follow-up data will be included for analysis even if some follow up data is incomplete. Every attempt will be made to ensure that there is as

little missing data as possible including reminder phone calls and follow-up phone calls, if a subject misses a visit.

The primary aim is to demonstrate non-inferiority of PAE compared to medication with respect to the outcome measure IPSS. We assumed a non-inferiority margin of 10%, in line with the FDA's recommendations, since similar prior non-inferiority trials were unavailable. The null hypothesis states that in the target population mean IPSS is at least 10% greater at 6 months post-treatment than at baseline (pre-treatment). The alternative hypothesis will be that the mean IPSS at 6 months is less than or equal to 10% greater than the mean IPSS at screening.

To address this hypothesis we will implement a random effects linear model, modeling IPSS score as a function of time and the indicator of whether medication had stopped by the time of the 3-month follow-up. We will include an R-side compound symmetric random effect to account for patient-level correlation. We will compute the predicted mean and standard deviation(SD) of IPSS at screening and 6 months; the difference of the predicted mean IPSS score, defined as the mean IPSS at 6 months minus the mean IPSS at screening; and the SD of this difference. Point estimates of these values will be reported along with 95% confidence intervals for the mean difference.

A non-inferiority p-value <0.05 testing whether the difference in the predicted mean at screening is at least 10% greater than the predicted mean of IPSS at screening will be considered evidence against the null hypothesis of inferiority of PAE, compared to treatment. A non-inferiority p-value >0.05 will be considered inconclusive evidence against inferiority.

As a sensitivity analysis for the primary aim, we will repeat the same model outlined above after removing patients from the analysis who were still taking medications at the 3-month follow-up. Point estimates, confidence intervals, and p-values will be compared against those obtained in the primary analysis.

To address the secondary aim, we will tabulate the proportion of patients AEs pre- and post-PAE, comparing the proportion using McNemar's test. A p-value <0.05 for McNemar's test will be considered evidence that the proportion of AE's differs for medication, compared to PAE. A p-value >0.05 will be considered inconclusive. We will assume that the adverse events that occur following PAE will be attributed to the procedure and not medication.

We will present the percentage of prostate infarcted at 6 months and the incidence of minor complications at 1 month descriptively, and calculate 95% confidence intervals. Post-acquisition segmentation software will be used to measure infarct volume.

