4.1.14 Criteria for Removal from Study

Subjects will be withdrawn from the study if a major complication occurs that prevents completion of PAE or the ability to complete the follow up visits.

Patients may also withdraw at any point at their discretion. Data will be included with an intent to treat analysis. Reasons for study withdrawal will be recorded.

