4.1.15 Follow-up for Withdrawn Subjects

If a subject withdraws from the study, any recorded data will still be included in the analysis. Subjects will only be replaced if they withdrew prior to undergoing PAE.

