9.3 Monitoring/Auditing

9.3.1 Data and Safety Monitoring Plan

Data and Safety Monitoring will be performed by a licensed physician who is not a study investigator.

The CRFs and any relevant source documents will be sent to the Study Monitor (as above) who will review them after treatment is complete for subjects 1, 10, 20 and 30.

Complications will be assessed by the co-PIs, categorized into major and minor categories and recorded on the CRF. CRFs and appropriate source documents will be made available to this individual for annually (every 12 months) review to ensure completeness of data collection. Any discrepancies will be immediately addressed by the co-PIs. All adverse events will be recorded and then summarized for inclusion in the final manuscript. Relatedness to the study

procedure will be assessed by an appropriately delegated investigator based on licensure.

Data monitoring will be performed by Study Monitor listed above. CRFs and appropriate source documents will be made available to this individual for bi-monthly review to ensure completeness of data collection. Any discrepancies will be immediately addressed by the co-PIs.

Because this is a small study with only 30 subjects, no DSMB will be used for this study. Data and safety monitoring will be conducted by an individual (Study Monitor) who is not an investigator on this study (see above).

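### Sections 4.1.14, 4.1.15 and 8.3 give conflicting analysis sets, so failed or abandoned PAE procedures can drop out of the primary comparison

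*Combined protocol and SAP*

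**What the plan says.** Section 8.3 makes a man evaluable if he gave written consent, "he meets the inclusion and exclusion criteria, and received the PAE study procedure". It then adds: "All subjects with 12-month follow-up data will be included for analysis even if some follow up data is incomplete". It does not say what happens to men without 12-month data, and gives no rule for a missing 6-month IPSS, which is the primary outcome in Section 2.3.1.

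Section 4.1.14 withdraws men if "a major complication occurs that prevents completion of PAE or the ability to complete the follow up visits". The same section says: "Data will be included with an intent to treat analysis". Section 4.1.15 says of a withdrawn man that "any recorded data will still be included in the analysis", and adds: "Subjects will only be replaced if they withdrew prior to undergoing PAE".

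Three other places bear on the point:
- Section 4.2.2 defines technical success as embolization of both sides, so procedures that fall short of this are foreseen.
- Section 8.1 stops the study after more than one major complication.
- Section 9.3.1 states: "All adverse events will be recorded and then summarized for inclusion in the final manuscript".

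**The concern.** The evaluable set in Section 8.3 consists of treated and eligible men. It is not an intent-to-treat set, and nothing says which rule governs. The deciding terms (received in 8.3, completion in 4.1.14, undergoing in 4.1.15) are undefined for a procedure that begins and then fails. In an unblinded single-arm study, that choice could be made after the result in the man concerned is known.

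Retaining recorded data does not remove the problem. A man withdrawn because of a complication during PAE will usually have a screening IPSS and no 6-month IPSS. The mixed model can keep his screening value, but he then adds almost nothing to the estimated change. In effect the model assumes he would have fared like the men who were followed. That is doubtful when his loss was caused by how PAE went. If omitted men do worse than average, the error favours PAE.

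**Working it through.** **Step 1. The rules side by side**

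| Man | Sections 4.1.14 and 4.1.15 | Section 8.3 |
|---|---|---|
| Withdraws before the procedure | Intent to treat would keep him; he may be replaced | Not evaluable |
| Arterial access, then abandoned with no embolization | Recorded data kept | Not settled |
| One side embolized | Recorded data kept | Probably received PAE, but not stated |
| Major complication prevents completion | Withdrawn; recorded data kept | Not settled; usually no 6-month IPSS |
| Treated, later found ineligible | Recorded data kept | Not evaluable |

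The sections agree clearly on none of these rows.

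**Step 2. The plan's own figure**

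Inputs from Section 8.2: PAE decrease 9.23, medication decrease 6.6, SD 5.7 at both times, correlation 0.65, 30 pairs with 20% dropout, alpha 0.025 (taken as one-sided).

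- Expected PAE advantage: 9.23 − 6.6 = 2.63.
- SD of the change: 5.7 × √(2 × (1 − 0.65)) = 4.769.
- Pairs analysed: 30 × 0.8 = 24, so SE = 4.769/√24 = 0.97.
- Paired t-test with distance to the margin of 2.63 × 1.10 = 2.893: power 81.22%, against the stated 81.2%.

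The figure reproduces and already allows for 24 of 30 pairs, so this point shows no error in it. It does imply a margin of 10% of 2.63, or 0.26 points, whereas Section 8.3 bases the margin on mean screening IPSS. That is a separate matter, but both readings are used in the verdict.

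**Step 3. How often the complication route would arise**

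Section 5.4 reports 2 major complications in 662 men (0.30%). I assume that definition matches the one in Section 8.1.

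- Expected in 30 men: 30 × 2/662 = 0.09.
- P(at least one) = 1 − (1 − 2/662)^30 = 8.7%.
- P(at least two) = 0.4%.
- At the exact upper 95% limit of 1.09%: expected 0.33, P(at least one) 28.0%, P(at least two) 4.2%.

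Not every major complication prevents completion or follow-up, so at each rate these are upper values for this route.

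**Step 4. Effect on the mean IPSS change**

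Let the other 29 men change by −2.63 on average and the omitted man by c. The mean without him is −2.63. The mean with him is (29 × (−2.63) + c)/30. Omitting him flatters the result by (c + 2.63)/30.

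- c = 0 (no change from screening on medication): 2.63/30 = 0.09 points.
- c = +6.6 (assumed: off medication, full drug benefit lost, nothing gained from PAE): 9.23/30 = 0.31 points.

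The effect adds up over men. Three omitted men, a purely illustrative number for technical failures, would give 3 × 2.63/30 = 0.26 to 3 × 9.23/30 = 0.92 points.

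**Step 5. Effect on the post-PAE adverse-event proportion**

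If one man with an event is omitted and k of the other 29 have events, the understatement is (k + 1)/30 − k/29 = (29 − k)/870. At k = 0 this is 3.3 percentage points, the maximum. At k = 14 (illustrative) it is 15/870 = 1.7 points.

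**The case against.** A reader might infer that failures are certain to leave both the efficacy and the safety results. The documents do not support that:

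- **Priority.** No passage makes Section 8.3 override 4.1.14 and 4.1.15. The intent-to-treat statement stands in the same section as the withdrawal rule. This stands: men can drop out, but the text does not say that they will.
- **Received and replaced.** Section 4.1.14 speaks of a complication preventing completion, so the procedure had begun. Such a man may well count as having received PAE, and is hard to describe as withdrawn before undergoing it. His replacement is therefore a weak reading. The terms are still undefined.
- **Adverse events.** A reader might infer that the worst complications vanish from the safety report. Section 9.3.1 summarises all adverse events, and Section 8.1 counts major complications for stopping. Only the McNemar comparison in Section 8.3 is exposed, if it is run on the evaluable set or needs a complete before-and-after pair.
- **Number of men.** A calculation with two or more major complications overlooks that the second one stops the study under Section 8.1.
- **Eligibility.** Section 3.2 assesses exclusion at baseline, so that condition does not depend on outcome by design. This largely stands, although a deviation found after treatment would still remove a treated man.

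The strongest objection is size. One omitted man is unlikely to change the conclusion. That limits the weight of the point, but it does not reconcile the three sections.

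**Conclusion.** The conflict is real and should be corrected, but its likely effect is small. By the cited rate, the complication route would probably involve no man or one man. One man moves the mean change by 0.09 to 0.31 points. The upper value rests on his being off medication with the whole 6.6-point benefit lost, which no passage states.

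The documents give no mean screening IPSS. At an assumed 15 to 20, the Section 8.3 margin is 1.5 to 2.0 points. The expected result then lies 2.63 + 1.5 = 4.13 to 2.63 + 2.0 = 4.63 points inside it, more than 4 standard errors of 0.97. On the narrower margin implied by the power figure, a shift of 0.31 exceeds the margin itself (0.26), but the expected distance to that margin is still 2.89 points.

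The exposure could be larger through technical failure without a complication, for which the documents give no rate. The case for change is that an exclusion tied to how the procedure went favours PAE and costs little to remove.

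**What to change.** Replace the rules in Sections 4.1.14, 4.1.15 and 8.3 with one definition:

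- The primary efficacy and adverse-event set is every man in whom arterial access for PAE was obtained, including one-sided or abandoned embolization and eligibility deviations found later.
- Replacement is allowed only before arterial access.
- IPSS and adverse-event collection continues after a major complication unless the man withdraws consent.
- The Section 8.3 sentence on 12-month data is removed, or reworded so that it cannot exclude men who lack those data.
- A sensitivity analysis counts attempted men with no 6-month IPSS as not improved. For the mean, use a change of 0, with +6.6 as a harsher value. Because Section 4.2.2 treats an unchanged score as clinical success, state that for that proportion these men count as failures.

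The cost is wording in three sections, some extra follow-up contact with men who would otherwise be withdrawn, and possibly a slightly less favourable estimate.

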2.0 STUDY OBJECTIVES

2.1 Primary Objective

The primary aim of this study is to determine if PAE will result in a reduction of urinary symptoms similar to medication in individual patients.

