2.3 Outcome Variable

2.3.1 Primary Study Outcome Variable

Reduction in IPSS at 6-month follow-up.

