3.1.3 Prostate gland measures \geq 50 grams measured by MRI, CT, or ultrasound

3.1.4 Currently taking BPH medications including either alpha blockers, 5-alpha reductase inhibitors or the combination of both for no less than 6 months

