4.2.2 Effectiveness Assessments

Technical success will be defined as bilateral prostatic artery embolization. This will be determined during the procedure. Clinical success will be defined as an IPSS score reported at the 6-month visit that is equal to or less than the pre-PAE baseline score. The size of the prostate will be measured by MRI at 6-month follow-up visit. IPSS, QoL, PVR and Qmax will be measured at 3, 6 and 12-month follow-ups.

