8.2 Sample Size Rationale

Prior studies have demonstrated larger decreases in IPSS scores using PAE, compared to medication alone. Abt found the mean decrease in IPSS to be 9.23 for PAE with standard deviations of IPSS scores being 5.7 at baseline and after treatment (18). Lepor found a decrease in IPSS attributable to medications of 6.6 (17).

We set a 10% non-inferiority margin and expect the correlation of IPSS scores between screening and 6-months to be high. Assuming a correlation of .65 we will have 81.2% power to test the non-inferiority hypothesis with an alpha of 0.025 for our 30 budgeted pairs, assuming 20% dropout (pairs=subjects given single subject study design).

Power calculations used PROC POWER, SAS, Version 9.4. This sample size is adequately large to address the study's primary aim with reasonably large power.

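### Section 8.3 has no pre-specified rule for concluding that IPSS fell, although 2.3.1 labels the primary outcome a reduction and 8.2 expects one

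*Combined protocol and SAP*

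**What the plan says.** Section 2.3.1 gives the primary outcome as "Reduction in IPSS at 6-month follow-up". The primary objective in 2.1 is to "determine if PAE will result in a reduction of urinary symptoms similar to medication in individual patients", and sections 4.1.1 and 8.1 call this non-inferiority to medication. Men enter while on drug treatment; inclusion criterion 3.1.4 reads "Currently taking BPH medications including either alpha blockers, 5-alpha reductase inhibitors or the combination of both for no less than 6 months". The screening IPSS is therefore the medication value.

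Section 8.3 turns the aim into a single hypothesis. The null is "The null hypothesis states that in the target population mean IPSS is at least 10% greater at 6 months post-treatment than at baseline (pre-treatment", and the alternative is that "the mean IPSS at 6 months is less than or equal to 10% greater than the mean IPSS at screening". The contrast is the predicted 6-month mean minus the predicted screening mean, reported with a 95% confidence interval. The only decision rule is a non-inferiority p-value below 0.05, with no statement of sidedness. The one sensitivity analysis repeats the same model without men still on medication at 3 months.

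Section 8.2 says "We set a 10% non-inferiority margin", uses an alpha of 0.025, and opens with "Prior studies have demonstrated larger decreases in IPSS scores using PAE, compared to medication alone". It cites falls of 9.23 points for PAE and 6.6 for medication.

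For individual men, 4.2.2 says "Clinical success will be defined as an IPSS score reported at the 6-month visit that is equal to or less than the pre-PAE baseline score".

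**The concern.** The label in 2.3.1 and the expectation in 8.2 both point to a fall in IPSS relative to the on-medication value. The test in 8.3 asks only whether IPSS is less than 10% higher. Nothing connects the two: there is no test against zero, no ordering of claims, and no rule for reading a confidence interval that lies wholly below zero.

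Two reporting problems could follow. A bare non-inferiority pass could be written up against 2.3.1 as a reduction, although the interval includes no change. And if PAE does better than the drugs, as 8.2 expects, that finding would be a claim chosen after the data were seen, in an unblinded single-arm study. A pre-specified second step would avoid both at no cost in alpha.

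**Working it through.** **Inputs from 8.2.** SD of IPSS 5.7 at both times; correlation 0.65; 30 subjects with 20% dropout, so 30 x 0.8 = 24 pairs; alpha 0.025, read as one-sided; falls of 9.23 (PAE) and 6.6 (medication). The method is a paired t-test with noncentral-t power.

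**The plan's own power figure.**
- SD of the difference = 5.7 x sqrt(2 x (1 - 0.65)) = 4.77.
- Expected further fall = 9.23 - 6.6 = 2.63.
- Taking the margin as 10% of that difference (0.263), the distance from the null is 2.63 + 0.263 = 2.893.
- With 24 pairs the power is 81.2%, which matches 8.2.

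Other readings tried do not match: 73.5% with 24 pairs and no margin, 83.1% with 30 pairs and no margin, 89.9% with 24 pairs and a margin of 10% of 6.6. The documents do not show the calculation, so this is a reconstruction. On it, 2.63/2.893 = 91% of the distance from the null is an expected fall below the medication value.

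**What a conclusion of a fall would require.** The upper limit of the two-sided 95% interval must be below 0.
- 24 pairs: SE = 4.77/sqrt(24) = 0.973; t = 2.069; observed fall needed = 2.069 x 0.973 = 2.01 points.
- 30 pairs: SE = 4.77/sqrt(30) = 0.871; t = 2.045; observed fall needed = 2.045 x 0.871 = 1.78 points.
- Power at a true fall of 2.63: 73.5% (24 pairs) or 83.1% (30 pairs). With 24 pairs it is 50.3% for a true fall of 2.0 and 83.9% for 3.0.

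**How far apart the two questions are.** The screening mean is not in the documents. I assume 15 to 25, so the margin as worded in 8.3 is 1.5 to 2.5 points, treated as fixed. At a margin of 2.0 and one-sided 0.025:
- non-inferiority is met when the observed change is below 2.0 - 2.01 = -0.01 (24 pairs) or 2.0 - 1.78 = +0.22 (30 pairs);
- a fall is shown only below -2.01 or -1.78.

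Results between those limits support non-inferiority but not a reduction. The gap equals the margin, so it exists for any positive margin.

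| Assumed screening mean | Margin | Probability of meeting non-inferiority at a true change of 0 (24 / 30 pairs) |
|---|---|---|
| 15 | 1.5 | 0.31 / 0.38 |
| 20 | 2.0 | 0.50 / 0.60 |
| 25 | 2.5 | 0.69 / 0.79 |

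If the p-value rule in 8.3 means one-sided 0.05, the range becomes 0.44 to 0.88. A true change of 0 lies inside the alternative, so these are not false-positive rates.

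**Alpha cost of a second step.** The test against zero is made only after non-inferiority is met, at the same level, so the overall one-sided error stays at 0.025. With a fixed positive margin, an upper limit below 0 is also below the margin, so the two steps cannot conflict.

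**The case against.** A reader might infer that the primary test is wrong because the trial can succeed without any reduction. The documents do not support that. Screening is on medication, the medication is due to be stopped by the 3-month visit (4.1.4), and the aim is to match the drug effect. An unchanged IPSS after PAE is then the result sought. The pass probabilities in the table describe that design; they do not show an error.

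A reader might also take 2.3.1 as setting a threshold of zero that 8.3 contradicts. It sits under outcome variables, names a measure and a time, and states no hypothesis; 2.3.2 uses the same style for the secondary outcomes. Section 4.2.2 does not help that reading either, since it counts an unchanged score as success for an individual man.

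The planned 95% interval is a fair further point. If published, it would show whether a fall had been established. What is missing is only a rule, fixed in advance, for what may be concluded from it.

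Two cautions about the remedy also stand. The level is unsettled: 0.025 in 8.2 against an unsided 0.05 in 8.3. If the latter is one-sided, a second step at the same alpha would not agree with a 95% interval rule. And the study is uncontrolled, with men still on medication kept in the primary model, so a fall could partly reflect PAE plus medication.

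**Conclusion.** The point holds as a gap in pre-specification, not as a fault in the primary test. Non-inferiority against 10% of the screening mean fits the aim and should decide the trial. The gap is that 2.3.1 calls the outcome a reduction and 8.2 expects one of 2.63 points beyond medication, while 8.3 offers no planned way to conclude it. The missing step would be worth having: its power at the plan's own expected difference is 73.5% with 24 pairs and 83.1% with 30. Those figures rest on the SD of 5.7, the correlation of 0.65 and one-sided 0.025. At a correlation of 0.5 they fall to 58.1% and 68.5%. The non-inferiority cut-offs rest in addition on an assumed screening mean and illustrate the gap only.

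**What to change.** 1. In 8.3, replace the unsided p-value rule with one-sided 0.025, which agrees with 8.2 and with the two-sided 95% interval. State the margin as 10% of the screening mean, and reconcile the power calculation in 8.2 with that margin.
2. Add a fixed sequence on the same 6-month-minus-screening contrast. Step one is non-inferiority, which decides the trial. Step two, taken only if step one is met, concludes that mean IPSS is lower than at the on-medication screening visit if the upper limit of the two-sided 95% interval is below 0.
3. If only step one is met, conclude that IPSS is not more than 10% worse than on medication, and do not report a reduction.
4. Reword 2.3.1 as the change in IPSS from on-medication screening to 6 months.
5. State that any step-two conclusion is a within-patient, uncontrolled change, to be read beside the planned sensitivity analysis that excludes men still on medication at 3 months.

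The cost is wording in 2.3.1, 8.2 and 8.3: no added patients, data or alpha. The only thing given up is the freedom to describe a bare non-inferiority pass as a reduction.

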4.1.4 Prior and Concomitant Therapy

The subjects will be required to have been on medical therapy for BPH for at least six months prior to undergoing PAE. Such medications include alpha blockers, 5-ARIs or combination therapy. The medication usage will be stopped by the 3 month visit in order to allow an adequate washout period for 5-ARI's prior to the 6 –month visit.

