4.1.10 Visit 5 - 3 Month Follow-Up

Subjects will return 90 +/- 14 days after PAE procedure to complete IPSS, and QOL questionnaires; to have Qmax and PVR measured; medication history questionnaires will be completed; and subjects will be evaluated for possible adverse events. It will be recorded if subjects are unable to hold medications at this time due to residual urinary symptoms. If an AE is suspected based on change in pain scores or functionality, an appropriate work-up will be performed.

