4.1.11 Visit 6 - 6 Month Follow-Up

Subjects will return 180 +/- 14 days after PAE procedure to complete IPSS with QOL and medication history questionnaires and to have Qmax and PVR measured. The subjects will be evaluated for possible adverse events. If an AE is suspected based on change in pain scores or functionality, an appropriate work-up will be performed.

An MRI of the prostate will be acquired.

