4.1.13 Subject Compliance Monitoring

Study coordinators and physicians will inquire of the subjects to determine if they have escalated any current or initiated any new conservative therapies during the follow-up period.

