4.3 Time and Events Table

	Visit 1 (Screening)	Visit 2 (Procedure)	Visit 3 (1 Day)	Visit 4 (1 week)	Visit 5 (3 month)	Visit 6 (6 Month)	Visit 7 (12 month)
Informed Consent	X						
MRI	X					X	
PAE procedure		X					
IPSS w/QOL	X				X	X	X
Qmax	X				X	X	X
PVR	X				X	X	X
Medication History Questionnaire	X	X			X	X	
AE Assessment			X	X	X	X	

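### As written, the month-3 medication indicator in Section 8.3 does not adjust the 6-month contrast for men still on BPH medication, and month-6 medication status is collected but not analysed

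*Combined protocol and SAP*

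**What the plan says.** All places are in the combined protocol and SAP.

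- **Intended state at 6 months (4.1.4).** "The medication usage will be stopped by the 3 month visit in order to allow an adequate washout period" for 5-ARIs ahead of the 6-month visit. The primary score is therefore meant to be off drug.
- **Foreseen failures (4.1.10).** "It will be recorded if subjects are unable to hold medications at this time due to residual urinary symptoms".
- **Primary model (8.3).** A random effects linear model with compound symmetric correlation, "modeling IPSS score as a function of time and the indicator of whether medication had stopped by the time of the 3-month follow-up". The tested quantity is the predicted mean at 6 months minus that at screening: "We will compute the predicted mean and standard deviation(SD) of IPSS at screening and 6 months". The section gives no interaction with time, no coding of the indicator at screening (when every man is on medication, by 3.1.4), and no level at which the means are predicted.
- **Only sensitivity analysis (8.3).** The same model "after removing patients from the analysis who were still taking medications at the 3-month follow-up".
- **Later medication data.** At Visit 6 men return "to complete IPSS with QOL and medication history questionnaires and to have Qmax and PVR measured" (4.1.11). The row "Medication History Questionnaire" in the 4.3 table is marked at Visits 1, 2, 5 and 6. Staff will also "inquire of the subjects to determine if they have escalated any current or initiated any new conservative therapies during the follow-up period" (4.1.13). No analysis in 8.3 uses any medication information after month 3.
- **Stated purpose (8.1).** Reduced medication use at 6 months is named as something the study will assess. Section 8.3 has no analysis of it.

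**The concern.** Each man is his own comparator: on medication at screening, after PAE and off medication at 6 months. A man still on medication at 6 months contributes PAE plus drug, which blurs the comparison the study is built to make. Someone reading Section 8.3 would take the indicator to be the adjustment for such men. On the plain reading it adjusts nothing in the tested difference.

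The month-3 exclusion analysis deals with men who never stopped, but not with men who stopped and restarted. At stake is the wording of a positive result: it could be reported as PAE matching medication when part of the 6-month score comes from medication.

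**Working it through.** **1. The plan's own figure.** Section 8.2 gives SD 5.7, correlation 0.65, 30 men less 20% dropout (24 pairs), alpha 0.025, and decreases of 9.23 (PAE) and 6.6 (medication). SD of the difference = 5.7 × √(2 × (1 − 0.65)) = 4.769. A distance of (9.23 − 6.6) × 1.1 = 2.893 gives paired-t power of 0.812, the stated 81.2%. This implies a margin of 0.263 points (10% of 2.63), which is inferred. Section 8.3 instead tests against 10% of the screening mean. The error rates below use the Section 8.3 margin throughout.

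**2. Cancellation.** Write E(Y at visit j, man i) = μ + τ_j + γS_i, with S_i the month-3 indicator. Six months minus screening is τ_6 − τ_0, and γS_i drops out. With complete data and compound symmetry the estimate is the plain paired mean.
- Check: 24 men, 4 visits, 5 men on a 6.6-point drug. Estimate 0.7464 and SE 0.9735, both with and without the indicator; raw paired mean 0.7464.
- With 20% of follow-up visits missing at random, the indicator moved the estimate by at most 0.15 points over 100 data sets. The shift from medication there was about 0.30 × 6.6 = 1.98.
- The indicator can also enter through 10% of a screening mean predicted at *stopped*. If 5 of 24 men differ by 3 points, that is 0.1 × (5/24) × 3 = 0.06 points.

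**3. Other readings.**
- *Interacted with time:* predicting at the sample average returns the unadjusted mean. Predicting at *stopped* returns the exclusion analysis. Equal weights on the two levels give neither.
- *Time-varying* (5 of 24 men on a 6.6-point drug at random, true off-drug change +1.5): with screening coded as on medication and both means predicted at *stopped*, the contrast is 1.5 − 6.6 = −5.1. With screening coded 0 it is +1.5. Predicted at observed values it is 1.5 − (5/24) × 6.6 = +0.1.

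Section 8.3 does not choose among these.

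**4. Size in the primary contrast.** Shift = q × b. Assumed: 24 pairs, SD 5.7, correlation 0.65, screening mean 15 (margin 1.5), off-drug truth exactly at the margin, men on medication at random, one-sided 0.025. The test is a paired t on Y6 − 1.1 × Y0, with 100,000 simulated trials. With nobody on medication the error is about 2.5%.

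| b (points) | 2 of 24 | 5 of 24 | 7 of 24 |
|---|---|---|---|
| 1.65 | shift 0.14; 3% | 0.34; 5% | 0.48; 6% |
| 3.3 | 0.28; 4% | 0.69; 8% | 0.96; 12.6% |
| 6.6 | 0.55; 6% | 1.38; 17% | 1.93; 31% |

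**5. The planned month-3 exclusion, no restarters, 2/5/7 men removed.** Error is about 2.5% if persistence is random and 2.2/2.0/1.8% if it follows the 3-month symptom level (2.9/3.4/3.8% at a 3-to-6-month correlation of 0.8). It is 6/13/18% if it strictly follows poor change by month 3.

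**6. Restarters: 4 men removed at month 3, and 4 of the 20 kept restart.**

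| b | Random restart, kept | Restart on poor 3-month change, kept | Same men excluded |
|---|---|---|---|
| 1.65 | 4.5% | 5.5% | 11% |
| 3.3 | 7% | 10% | 11% |
| 6.6 | 13.5% | 22.5% | 11% |

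Excluding restarters brings the error back to about 2.4% only when restarting is random.

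**The case against.** The strongest reply is that the plan already handles medication. It requires stopping by month 3, records failures to stop, and excludes those men in a sensitivity analysis. That analysis is close to unbiased if persistence is random or follows the 3-month symptom level, which is roughly what Section 4.1.10 describes. Keeping every observed score is also a legitimate treatment-policy analysis, consistent with the intent-to-treat statement in 4.1.14. All of this stands. What remains is that the plan does not say its conclusion concerns PAE with or without medication, that the indicator is not the adjustment it appears to be, and that restarting is not covered.

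Four stronger readings are tempting, and the documents do not support them.
- *The primary test is invalid.* It is valid for the treatment-policy question; only the claim about PAE alone is affected.
- *The indicator is useless under any specification.* The cancellation belongs to the additive, per-patient reading with complete data. Other specifications change the contrast, but none is stated.
- *A 17% or 31% error is to be expected.* Those figures take b = 6.6, which Section 8.2 gives as the effect of medication, not as an added effect after embolization. They also put the truth at the margin, whereas Section 8.2 plans on PAE being 2.63 points better. If that holds, non-inferiority is correct for PAE alone as well.
- *Excluding men on medication at month 6 would repair the problem.* It selects on outcome after PAE and can be worse than keeping them, as the last table shows.

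**Conclusion.** The concern holds in limited form. On the plain reading of Section 8.3, the month-3 indicator leaves the tested difference unadjusted for men still on medication. Men who restart after month 3 are treated as stopped in both planned analyses, although Visit 6 would identify them. The direction is toward non-inferiority for PAE alone, by q × b.

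The size is uncertain. Under the stated assumptions, error against a nominal 2.5% runs from about 3% (2 men, b = 1.65) to an upper bound of 31% (7 men, b = 6.6). The share on medication, the drug's effect after PAE, the restart rate and the screening mean are all assumed. The cancellation needs none of these assumptions. Severity: minor to moderate.

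**What to change.** 1. State that the primary observed-score contrast estimates *PAE with or without medication*, and word its conclusion that way.
2. Drop the main-effect indicator, or specify it as interacted with time or time-varying. In either case give its coding at screening and the level or weights at which each mean is predicted.
3. Add a reported, non-gating tipping-point analysis: add delta, over a range from 0 to 6.6, to the 6-month score of each man on BPH medication at month 6, and report where non-inferiority is lost. Treat men who stopped a 5-ARI after month 3 as a separate variant, since Section 4.1.4 ties the washout concern to that class.
4. Keep the month-3 exclusion analysis. If men on medication at month 6 are also excluded, report that only beside the delta analysis, and state that it selects on outcome after PAE.
5. Report the proportion off medication at 6 months, which Section 8.1 names as a purpose.

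**Cost.** Revised wording and a little extra analysis. No new data are needed, because medication status at months 3 and 6 is already scheduled. The primary test keeps its power because nothing new gates it. The downside is a narrower claim if many men remain on medication. The delta analysis should not be pass/fail. On the same 1.5-point margin, with a true change of −2.63, power is about 97%. If the drug in fact adds nothing, the result would survive delta = 6.6 in only 89/63/41% of trials with 2/5/7 men on medication.
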